#### **6.3 Electronic Informed Consent (eConsent)**

To accommodate any current and future local restrictions on enrollment into research studies during COVID-19, and other similar circumstances, sites should comply with local practices/guidance regarding informed consent procedures. If informed consent can be obtained remotely (i.e., by eConsent) through a secure and locally approved platform (e.g., RedCap, Docusign, etc.), sites should get IRB approval to do so. All eConsent procedures should be documented according to local procedures, and included in the participant's study record in the TRACK-TBI electronic database (i.e., QuesGen).

## **6.4 Competency Screening and Legally Authorized Representatives**

TBI often results in a period of posttraumatic amnesia (PTA) characterized by confusion, disorientation, and impaired memory for ongoing events. Thus, TBI patients will be screened for competency using the Galveston Orientation and Amnesia Test (GOAT) to determine whether they are competent to provide informed consent

or whether this must be done by a Legally Authorized Representative (LAR). This competency screening will be performed prior to inviting the subject to participate in the study and while the subject is in the ED or hospital.

The procedure for this competency screening will be:

- 1. The subject's ED medical record will be reviewed to determine whether the subject has been diagnosed with post-traumatic amnesia or other cognitive deficits.
- 2. The subject and family, if present, will be approached and informed about the study.
- 3. If subject and family agree, the GOAT will be administered according to standard procedures.
  - a. If the subject scores ≥75 on the GOAT, the subject will be deemed competent to provide informed consent.
  - b. If the subject scores <75 on the GOAT, then informed consent must be provided by a LAR.

### 6.5 Language and Literacy

Subjects should be fluent in English to be eligible for the study. Sites with research personnel fluent in Spanish may elect to enroll patients who speak Spanish as their primary language. The informed consent documents are available in both English and Spanish. Patients not fluent in English, or Spanish at certain sites, will be ineligible for the study.

#### 6.6 Need for Re-consent

As this is a longitudinal study with multiple assessment time points over the course of 3 months, and knowing that the status of TBI patient cognition may change over this time course, it is likely that subjects may not recall all of the activities or procedures associated with each follow-up visit. To ensure that subjects are still willing to participate, the research personnel will review the Informed Consent document with the subject at the beginning of each follow-up visit.

In the event that a subject was determined incompetent to sign their informed consent document (i.e., GOAT score <75 at time of screening/consent) but later demonstrates competency, then the subject will be asked if they wish to continue participation. If so, then the subject will be asked to sign the Informed Consent Form at that time. If they decline to do so, they will be withdrawn from the protocol.

## **6.7 Storage of Consent Documents**

Signed paper consent forms will be stored in a locked file cabinet located in the study office behind locked doors at each site. These documents will be stored for a minimum of 5 years after the conclusion of the study. These documents will be made available, as needed, for review for quality monitoring purposes.

## 6.8 Waiver of Consent

Sites may elect to enroll qualifying patients initially incapable of informed consent who have no legally authorized representative available for LAR consent. This can be done under a "waiver of consent" rule in the emergency setting in order to procure and process all study blood collections. While UCSF will serve as the single IRB (sIRB) for this study (further details about this below), each site who signs on to the study will be able to determine, independently, if they will implement the Waiver of Consent at their local site. This protocol meets all "Waiver of Consent" criteria under 45 CFR 46.116(f) (3):

- (i) The research involves no more than minimal risk to the subjects;
- (ii) The research could not practicably be carried out without the requested waiver or alteration. Our research team has extensive experience conducting research in this population; TBI patients very frequently present alone (without a LAR) and with alteration of mental status (ranging from mild disorientation to coma) limiting capacity for self-consent due either to their acute injury or other contraindications.

- (iii) The research could not practicably be carried out without using information or biospecimens in an identifiable format. We need to collect identifiable private information (such as patient name, medical record number, and contact information) from patients under waiver so that we can extract data from the EMR, contact a LAR to provide consent as soon as possible, and so that we can complete additional longitudinal follow-up timepoints with the patient/LAR and link this data to previously collected data) in the event that informed consent is obtained;
- (iv) The waiver or alteration will not adversely affect the rights and welfare of the subjects. The primary risks of this observational study is loss of privacy and standard risks associated with a blood draw. We have taken steps to ensure the privacy of subjects. In most cases, blood draws will be collected through already placed arterial lines and/or at the same time of clinically indicated blood draws, and thus, there will be minimal to no additional risks associated with these blood draws. Furthermore, in the event that patient or LAR consent cannot be obtained by the time of the 2 week study visit, all data collected on the patient, including blood collected and processed, will be discarded (will not be analyzed, banked, or shared with collaborators); (v) Whenever appropriate, the subjects or LAR will be provided with additional pertinent information after participation. We will make every effort to obtain patient or LAR consent as soon as possible after enrollment under waiver. A copy of the consent form as well as a study summary document that summarizes the pertinent details about the study will be left at the bedside of a patient enrolled under Waiver of Consent, and study staff will stay in touch with hospital staff to monitor the patient's status while inpatient. If a patient is discharged while still under waiver, then the patient will be discharged with a copy of the consent form, a study summary document that summarizes the pertinent details about the study, and contact information for study staff. Study staff will approach in-person (if the patient remains inpatient/the LAR presents to the bedside) or by phone (if the patient is discharged/a LAR is identified who is off-site) to complete the informed consent process as soon as the patient may be able to consent for her/himself and/or a LAR presents her/himself. If self or LAR consent is not obtained by the time of the 2 week study visit, then all data and blood collected under waiver will be destroyed/discarded.

Suggested IRB language: If an eligible TBI patient presents to our hospital who is not capable of selfconsent, and there is no LAR identified, then a 'Waiver of Consent' will be used to collect baseline clinical data and study blood draws (most critically, the baseline blood draw must be within 6 hours of injury and ideally as soon as possible after injury). Specifically, we will complete study blood draws, blood processing and freezing in our local freezer, and collection of baseline clinical data (including data from the EMR and head CT imaging that was obtained as part of routine clinical care) without consent if the subject does not have the capacity to provide consent and there is no LAR identified. The blood taken under waiver could be the 6-hour, 12-hour, and 24-hour blood draws. Each blood draw is 16.0 mL and this will total 48 mL of blood taken under waiver. If the patient cannot provide consent or an LAR has not been identified to provide consent by the two week timepoint then the patient will be removed from the study. We anticipate that most of the patients we enroll will have a line placed and we will ask for the draw through this. If unavailable, we will ask the nurse to complete the blood draw with a stick. The collected blood will NOT be analyzed in any way (either proteomic or genetic analyses), shared with collaborators, or sent to the National TBI Biorepository (NTBI-BR) at the University of Pittsburgh Medical Center without informed consent from the patient or LAR. Research MRIs will not be completed without consent. If an MRI is not completed within the first 48 hours, the patient will be eligible to remain in the study. In the event that the patient remains incapable of selfconsent or a LAR is not identified by the time of the 2 week visit, then all clinical data will be destroyed and all collected blood samples will be discarded. If the patient regains capacity to consent or a LAR is identified before the time of the first follow-up and s/he declines future participation in the study, then the patient/LAR will then be given the opportunity to provide informed consent to permit the use of any already-collected clinical data and/or blood (that was collected under waiver) for research purposes. If the patient/LAR consents to the use of already collected data, then s/he will sign the informed consent form but will then be documented as electively withdrawing from future participation in any additional

follow-up data collection. If consent is not obtained prior to the patient's discharge, they can be contacted with the Verbal Consent Script to describe the study objective and voluntary nature. If they are interested in the study, the research staff will explain the study in full over the phone. If they agree to participate, they will be mailed hard copies of the informed consent packet, emailed the informed consent packet, and/or asked to sign the informed consent using DocuSign.

## 6.9 Single Institutional Review Board (sIRB) and Human Research Protections Office

As of January 2020, all federally-funded studies are now required to use a Single Institutional Review Board (sIRB). UCSF will serve as the sIRB for this TRACK-TBI Precision Medicine protocol. Participating sites will rely on UCSF as the IRB of Record for this protocol. The UCSF Lead Coordinating Site Study Team is responsible for securing initial IRB approval from UCSF for this MSP (Master Study Protocol) and all other study documents such as the Informed Consent Form, any recruitment materials, and all study Standard Operating Procedures (SOPs) that describe the procedures and operations of the study as they pertain to enrolled subjects. Other sites cannot be added to the protocol until UCSF has initial approval for the study. The UCSF Lead Coordinating Site Study Team will utilize the online SMART IRB system to request, track, and document reliance on UCSF IRB for each Relying Site under the SMART IRB Agreement.

All relying sites' Study Teams will use the Informed Consent Form template(s) provided by the UCSF Lead Coordinating Site Study Team. Site Study Teams will provide any site-specific informed consent form language required for local study team contact details, compensation for injury, study participant reimbursement, etc. The Site Study Team will incorporate these site-specific changes to the Informed Consent with tracked changes, and will provide this form to the UCSF Lead Coordinating Site Study Team for submission to UCSF IRB.

The UCSF Lead Coordinating Site Study Team will be responsible for submitting amendments to the MSP as well as any unanticipated events, protocol deviations, adverse events, and annual continuing reviews, in accordance with UCSF IRB's established procedures and policies. The UCSF Lead Coordinating Site Study Team and participating relying Site Study Teams will follow the procedures as set forth in the UCSF sIRB Standard Operations Procedures (See "sIRB SOP for sites v2.2" on the Study Shared BOX folder at "Box\TRACK-TBI Precision Medicine Study Documents\Regulatory\IRB\sIRB SOP for all sites).

After IRB approval is obtained, the approved master study protocol (MSP) and supporting documents will be submitted to the Department of Defense Human Research Protection Office for review. Human subjects research cannot begin at a site until HRPO approval has been obtained.

#### **7 SUBJECT PROCEDURES BY CORE**

#### 7.1 Clinical

The following broad categories of clinical data variable types will be collected from all enrolled patients through medical record and personal interview:

- Baseline demographics e.g., age, gender, race, ethnicity, handedness
- Baseline socioeconomics e.g., education, employment, living situation, types of support
- Baseline medical history by system including substance abuse, prior TBI, and medications
- Mechanism of injury, location, and surrounding circumstances
- Pre-hospital clinical course variables e.g., vital signs, transport times, GCS score
- Brain CT report including presence of skull fracture and intracranial abnormalities
- Emergency department clinical course e.g., vital signs, GCS, fluids, labs, toxicology, complications
- Hospital admission clinical course e.g., complications, surgeries, neuromonitoring

- Hospital daily therapeutic intensity level for ICU patients with neuromonitoring
- Admit and discharge dates and times throughout full clinical course
- Abbreviated Injury Scale (AIS) score and Injury Severity Score (ISS)
- Discharge destination and acute care outcome evaluation

#### 7.2 Biospecimens Procedures.

We will obtain 12.0 ml of blood at each of the following time points: within 6 hours of injury, and again at 12h, 24h, 2d, 3d, 5day, 2w, 6w and 3m post-injury (See **Table 6**: Biospecimen Sample Collection Schedule below). Every blood draw will be optional. The TRACK-TBI Precision Medicine procedures around collection, processing, storage, and shipping of biospecimens collected during the in-person assessment will align with the TRACK-TBI U01 procedures (see Appendix 2: TRACK-Precision Medicine\_Biospecimen Protocol\_MOP\_v1.5\_APR062021, also saved on the Study Shared BOX folder at: TRACK-TBI Precision Medicine Study Documents\Biospecimens core\Biospecimens MOP).

- Collection at each time point will consist of one 6.0 ml lavender EDTA tube (plasma and buffy coat) and one 6.0 ml red top tube (serum).
- Whole blood will be processed for serum, plasma, and buffy coat. Serum and plasma will be stored in 500 µl aliquots for future analyses.

**Table 6**. Biospecimen Sample Collection Schedule

<6	12	24	Day	Day	Day	Day	Day	Day
hr	hr	hr	2	3	5	14	42	90
12	12	12	12	12	12	12	12	12
mL	mL	mL	mL	mL	mL	mL	mL	mL
	hr 12	hr hr 12 12	hr         hr         hr           12         12         12	hr         hr         hr         2           12         12         12         12	hr         hr         hr         2         3           12         12         12         12         12	hr         hr         hr         2         3         5           12         12         12         12         12         12	hr         hr         hr         2         3         5         14           12         12         12         12         12         12         12	hr         hr         hr         2         3         5         14         42           12         12         12         12         12         12         12         12

## Total blood volume that may be collected in 3 month period=108 ml

- At some sites (subject to IRB approval), cerebrospinal fluid (CSF) will be drawn for patients with
  ventricular catheters. The CSF collection protocol is detailed in TRACK TBI Precision Medicine Manual
  Of Procedures (see Appendix 2: Section 6 of TRACK\_Precision Medicine\_Biospecimen
  Protocol\_MOP\_v1.5\_APR062021, also saved on the Study Shared BOX folder at: TRACK-TBI Precision
  Medicine Study Document\Biospecimens Core\Biospecimens MOP). This is a site-specific protocol
  item.
- Specimens will be kept indefinitely until they are used up or destroyed, and may be used in future research unrelated to this study.

## Analysis.

A subset of the most promising DAI, MVI, and neuroinflammation blood-based markers identified previously in Phase 1-Base (under a separate IRB protocol) will be analyzed in this cohort. In addition, neuronal injury (UCHL-1) and astroglial injury (GFAP) biomarkers will also be assayed in these subjects.

## 7.3 Neuroimaging

## Clinical Care Neuroimaging Acquisition

CT or initial MRI will be obtained as part of clinical care. The subject may be transferred to the study hospital from another hospital at which an initial CT/MRI was already performed. In this case, the site must have the initial image available for collection in order to enroll. All initial and follow-up brain CT scans, and any brain MRI scans that are collected for clinical care will be acquired along with the radiology reports. Images will be read and coded by the Neuroimaging Core radiologist in accordance with the NINDS Neuroimaging TBI-CDEs.

#### MRI Procedures

In this cohort, we will obtain 3T MRIs within 2 week of injury (early), and for a subset of 20% of patients, an additional ultra-early MRI within 48 hours of injury. All patients will also receive a follow-up MRI at 3m post-injury. The overall MRI protocol is based on established TRACK-TBI standards for structural imaging, DTI and rs-fMRI that have been harmonized across 3T scanners from all 3 MR vendor platforms. Standard operating procedures for acquisition, QA, QC, and data management of this 3T MRI protocol will align with the TRACK-TBI U01 procedures. Participants will undergo the same MRI procedures as set forth in the TRACK U01 study (See Appendix 1: Precision Medicine-Neuroimaging MOP v1.1-03102021.docx, also saved on Study Shared BOX folder at: TRACK-TBI Precision Medicine Study Documents\Neuroimaging Core\ Neuroimaging MOP) with a few modifications. In addition to volumetrics, DTI and rs-fMRI, the new MRI protocol will incorporate novel imaging measures of axonal density (using neurite density index (NDI) from NODDI analysis of multishell diffusion MRI), cerebral blood flow (using ASL perfusion), and neuroinflammation (using free water content (FISO) from NODDI analysis of multishell diffusion MRI), which will all be standardized across sites and MRI vendors prior to participant enrollment.

The proposed MRI protocol includes one additional sequence not represented in the original TRACK-TBI protocol: ASL perfusion imaging of cerebral blood flow (CBF), as well as an additional 64-direction diffusion-weighted shell for the DTI protocol at b=3000 s/mm2 to create the multishell diffusion MRI sequence.

Arterial Spin Labeled Perfusion MRI Protocol: The ASL perfusion protocol is adopted from the new Alzheimer Disease Neuroimaging Initiative 3 (ADNI3) standards for all 3 MR vendors. In brief, the 5-minute sequence consists of 3D pseudo-continuous ASL (PCASL) on 3T GE scanners and 2D pulsed ASL (PASL) on Siemens and Philips scanners, with an additional proton density reference scan using the same ASL readout at a longer TR. These ASL acquisitions for all 3 MR vendor platforms conform to the most recent best practice guidelines for ASL perfusion imaging reported by the International Society for Magnetic Resonance in Medicine.44

The entire proposed MRI protocol can be acquired in 60 minutes. The de-identified neuroimages from each site will be uploaded to the neuroimaging core repository at UCSF.

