## MRI Analysis

We will incorporate axonal density from NODDI analysis of multishell diffusion MRI as an advanced microstructural imaging biomarker of both acute DAI and long-term white matter degeneration. Axonal density, measured as the neurite density index (NDI) of white matter from NODDI, is a metric of the intracellular volume fraction and is not affected by changes in the free water fraction. Therefore, it is a more specific biomarker of axonal loss than any DTI metric such as FA, MD, AD, or RD. In addition, we will incorporate a quantitative imaging biomarker of MVI, specifically, CBF using ASL perfusion MRI.

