#### MRI Statistical Considerations

We will calculate Pearson's correlation of each of the baseline early (<6 hours to 1 week) blood-based biomarkers, with the corresponding MRI markers that look promising based on Phase 1 results. There will be no adjustment for multiple comparisons as these comparisons are exploratory given the paucity of information about the time-course of these markers in people with TBI. ROC analysis will be performed to determine the discriminative ability of the blood-based and imaging biomarkers in predicting outcomes. AUC will be calculated and reported along with 95% confidence intervals. Prediction increment will be measured by change in AUCs calculated based on logistic regression models.

Adequacy of sample size: With 50 participants, using correlation power analysis, we have at least 80% power to detect a correlation of .38 or greater.

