# 14.3 Neuroimaging (See Appendix 1: TRACK-TBI Precision Medicine Neuroimaging MOP for detailed neuroimaging procedures)

Standardization of MR across sites. All study MR systems will initially be characterized with the Magphan® Quantitative Imaging Phantom (Phantom Laboratory, Salem, NY) designed to measure signal-to-noise ratio, object size scaling, and spatial distortion. The Magphan® Phantom has been extensively used for high-resolution structural brain imaging in numerous trials, including ADNI, as follows:

- 1. Serial imaging of the phantom will track scanner performance over the study enrollment period using an online MR Distortion and Image Quality service (ImageOwl, Salem, NY) which identifies scanner errors or defects and corrects for scaling errors and gradient non-linearity.
- 2. Standardization for diffusion MR imaging using an ice water phantom adopted by ACRIN for multi-site diffusion imaging trials.
- 3. Performance of fMRI will be assessed using the Biomedical Informatics Research Network (BIRN) phantom, with serial data analyzed to assess signal mean and standard deviations, temporal fluctuations, and drift.

Standardized MR protocols will maximize consistency among study sites and across vendor platforms. Within vendors the protocols will be identical and shared via manufacturer-generated tools (e.g. edx files, examcards). Across vendors, protocols will match spatial coverage, voxel dimensions, and primary contrast parameters (e.g. echo time, repetition time). A TRACK-TBI board-certified neuroradiologist will evaluate the test-retest scans from all sites to assure diagnostic image quality and for pathoanatomic analysis of structural MRI sequences.

Neuroimaging Repository. All study neuroimages (CT and MRI) will be de-identified at each study site before uploading to the TRACK-TBI neuroimaging core repository (Flywheel) as DICOM files, utilizing the Neuroimaging Core's de-identification and transport protocol. Image data will then be passed into one of a series of modality-specific semi-automated quality assessment pipelines and evaluated by the Neuroimaging Core for protocol conformance and quality. QA results will be provided to acquisition sites within 48 hours and

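### Cerebral blood flow is acquired by two ASL methods tied to scanner vendor, but the planned blood–CBF correlation is a plain Pearson coefficient with no term for ASL method

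*Protocol*

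**What the plan says.** All of this is in the Protocol.

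- **Acquisition (7.3, MRI Procedures).** The ASL sequence "consists of 3D pseudo-continuous ASL (PCASL) on 3T GE scanners and 2D pulsed ASL (PASL) on Siemens and Philips scanners". Labelling and readout therefore both change with the vendor. The novel measures, CBF among them, are ones "which will all be standardized across sites and MRI vendors prior to participant enrollment".
- **Cross-vendor control (14.3).** "Across vendors, protocols will match spatial coverage, voxel dimensions, and primary contrast parameters". The section describes phantoms for structural, diffusion and functional imaging. It names none for perfusion, and no harmonisation of CBF after acquisition.
- **Role of CBF (7.3, MRI Analysis).** "we will incorporate a quantitative imaging biomarker of MVI, specifically, CBF using ASL perfusion MRI". Table 1 also lists SWI as an imaging marker of microvascular injury.
- **Analysis (7.3, MRI Statistical Considerations).** The statistic is named in its opening sentence: "We will calculate Pearson's correlation of each of the baseline early (<6 hours to 1 week) blood-based biomarkers, with the corresponding MRI markers". The imaging side is restricted to those "corresponding MRI markers that look promising based on Phase 1 results". No term for vendor, ASL method or site is named. The statement that nothing will be adjusted concerns multiple comparisons only. ROC analysis and logistic models for outcome prediction are planned as well.
- **Size (same paragraph).** At least 80% power for a correlation of .38 with 50 participants.
- **Sites (3.2 and 14.1).** Five sites. The scanner vendor at each is not given.

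**The concern.** A Pearson coefficient over all patients treats CBF as one measurement. If PCASL and PASL values differ systematically, part of the CBF variance is only a difference between scanner groups. That variance is unrelated to the blood marker and pulls the pooled coefficient towards zero.

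Patients are also nested in sites, and each site has its own scanner and case mix. If sites using one method also enrol patients with higher or lower blood markers, the two group differences line up. The pooled coefficient can then depart from zero with no association inside either group. A real blood–CBF association could be missed, or a scanner contrast taken for one, in a study meant to validate imaging markers for later trials.

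**Working it through.** **1. The Protocol's own figure.** By the Fisher z approximation, power = Φ(atanh(r)·√(n−3) − 1.96). Alpha is not stated, so two-sided 5% is assumed. With r = .38 and n = 50: atanh(.38) = 0.400, √47 = 6.856, product 2.743, power = Φ(0.783) = 0.783. Simulation with the t-test gives 0.793. The stated 80% is reproduced to within two points.

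**2. Inputs the documents do not give (all assumed).** f = share of patients on PCASL; d_y = CBF offset between methods; d_x = blood-marker difference between the method groups. Both differences are in within-group SD. The main case is f = 0.4, so f(1−f) = 0.24.

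**3. Formula.** Pooled r = [ρ + f(1−f)·d_x·d_y] / √{[1 + f(1−f)·d_x²]·[1 + f(1−f)·d_y²]}, where ρ is the within-method correlation.

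**4. Dilution (ρ = .38, d_x = 0).** For example, at d_y = 1: r = .38/√1.24 = .341, and power = Φ(0.355 × 6.856 − 1.96) = 0.683. Each simulated column value comes from two separate runs of 20,000 studies.

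| d_y (SD) | pooled r | power, Fisher z | power, simulated |
|---|---|---|---|
| 0.5 | .369 | 0.757 | 0.764, 0.768 |
| 1.0 | .341 | 0.683 | 0.689, 0.692 |
| 1.5 | .306 | 0.583 | 0.589, 0.583 |

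With f between 0.2 and 0.5, a 1 SD offset gives power of 0.68 to 0.72.

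**5. False positives (ρ = 0).** With d_x = 0 the numerator is zero and simulated rejection stays at about 0.05 for every CBF offset tried. With d_x = 0.5 and f = 0.4:

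| d_y (SD) | pooled r | rejection rate, simulated |
|---|---|---|
| 0.5 | .057 | 0.069 |
| 1.0 | .105 | 0.114 to 0.115 |
| 1.5 | .141 | 0.163 to 0.164 |

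**6. After adjustment.** A partial correlation with k adjustment terms uses √(n−3−k).

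- ASL method (k = 1): Φ(0.400·√46 − 1.96) = 0.774. Simulated null rejection returns to 0.050 to 0.054.
- Five sites (k = 4): Φ(0.400·√43 − 1.96) = 0.746.

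**The case against.** The strongest reply is that the Protocol promises standardisation before enrolment. It follows an established three-vendor ASL standard and published guidance, adds a proton density reference scan, sends images through modality-specific pipelines, and leaves detail to a neuroimaging manual that is not at hand. Standardised need not mean one pulse sequence. Covariates could also sit in an analysis plan that is not shown, and the analysis is described as exploratory.

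Part of this stands. The following stronger readings are tempting, but the documents do not support them:

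- **That raw CBF values are pooled.** This is an inference from silence; no section says so.
- **That the difference in method creates correlations by itself.** It does not. The blood marker must differ between the method groups too.
- **That the loss is certain.** The vendor mix and the offset are unknown. If all sites use one method the problem disappears, and at 0.5 SD the power loss is about two points.
- **That every MRI marker is affected.** Structural imaging, DTI and rs-fMRI are described as harmonised across vendors, and phantoms are named. CBF enters the correlations only if it passes the Phase 1 filter, and ASL was not in the original TRACK-TBI protocol.
- **That Pearson correlation is the only analysis.** ROC and logistic analyses are also planned.
- **That skewed concentrations cost power.** The documents give no figure for skewness, so no shortfall can be claimed.

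The defence does not dispose of the core. The Protocol did not leave the statistic open: it named one without an adjustment term and sized the study on it. The cross-vendor measures it lists do not mention labelling or readout, which are what differ between the methods.

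**Conclusion.** The point holds in a conditional form. Two ASL methods are prescribed by vendor, nothing stated makes their CBF values comparable, and the named coefficient cannot absorb a difference between them. If both methods are in use and an offset remains, power at r = .38 falls from about 78% to about 76%, 69% or 59% for offsets of 0.5, 1.0 or 1.5 SD at a 40/60 split. False positives reach about 7%, 11% or 16% only if blood markers also differ by 0.5 SD between the groups. The split, the offsets and the marker difference are all assumptions. The effect is confined to pairs involving CBF. The case for changing the plan rests on how little the protection costs, not on a demonstrated bias.

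**What to change.** In MRI Statistical Considerations, for pairs involving CBF, replace the plain Pearson correlation with a partial correlation adjusted for ASL method, and add a site-adjusted version as a sensitivity analysis. State in MRI Procedures or section 14.3 how PCASL and PASL values are made comparable.

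Show CBF results by method for description only. At a 40/60 split the groups would be 20 and 30 patients, with Fisher z power at r = .38 of about 38% and 55%, too low for separate tests.

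The cost is wording and one degree of freedom: power at r = .38 goes from 0.783 to 0.774, or to 0.746 with four site terms. No new data are needed.

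As a secondary, inexpensive safeguard, log-transform blood concentrations if they prove skewed, with Spearman's correlation as a check. Results would then be read on the log scale.
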